Official title of the study:

Implementation of the Individual Danish Emergency Process Triage (I-DEPT)

Statistical analysis plan

Original version: June 14, 2022, Latest revised version: January 24, 2023 Latest upload date/Document date: March 30, 2023

Clinical trials registration: NCT04571021

Principal Investigator (PI) [name]^{1,2}, M.D., D.M.Sc., Co-PI [name].

Chief Statisticians

[name], [name].

Contributors to analysis and interpretation of data

Statisticians, Primary Investigators and Steering Committee

This document contains the statistical analysis plan for the I-DEPT study. The statistical analysis plan has been completed prior to the availability of the outcome data and aims to clarify the analyses.

Short summary

Triage systems have been implemented in most emergency departments (ED) to minimize crowding and treatment delays that can result in adverse patient outcomes. Triage systems with limited room for clinical judgment are used by emergency departments (EDs) worldwide. The Individual Danish Emergency Process Triage (I-DEPT) is a new simplified triage system with a clinical assessment. I-DEPT is designed to simplify risk prediction and to reintroduce clinical judgment as the central part of triage. In this trial we compare I-DEPT with a traditional triage model in terms of risk prediction and patient outcomes, with a focus on 30-day mortality. Intervention: I-DEPT is a new triage system constructed from data collected from 12 000 ED patient visits at a large Danish hospital. I-DEPT solely consists of a quick score of vital signs followed by a basic clinical assessment by an ED nurse. The final triage level results from a score calculated after measurement of vital signs corresponding to a triage level of 1-4, that is then adjusted by the ED nurse, who can either up-triage (up to 2 steps) or down-triage (1 step) according to clinical assessment with no specific explanation needed. The development of the I-DEPT (former called Copenhagen Triage Algorithm, CTA) has previously been described in detail (1). I-DEPT has previously been compared to the Danish Emergency Process Triage (DEPT) which is a local adaption of Adaptive Process Triage. The two triage systems were compared in a noninferiority, two-center cluster-randomized crossover study, where I-DEPT was non-inferior to a traditional triage algorithm by short term mortality, and superior in predicting 30-day mortality (2).

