Control: DEPT; is a local adaption of the Adaptive Process Triage (ADAPT), triage model developed in Sweden in 2006 like most other well-known triage models, was the standard triage model used in the study. It includes the presenting (or chief) complaint in addition to a list of vital signs with cut-off values corresponding to each triage level. These are both registered, and the final triage level is determined by the most urgent triage level assigned Both triage systems identify five levels of urgency with colors (red, orange, yellow, green, and blue). The least urgent of these (the fifth level) was excluded from this study as it is defined as non-emergent patients (e.g. minor injuries) and includes no indication for measuring vital signs.

Aim of the study

The aim of the study is to investigate the impact of I-DEPT that has a systematic involvement of clinical assessment and the possibility to adjust the triage. I-DEPT will be compared to the existing DEPT with a focus on mortality, critical illness/distribution within risk groups and time to assessment

Hypothesis

The main hypothesis is that I-DEPT will be non-inferior to the existing DEPT regarding 30-day mortality.

Timeline

The study will start at October 1, 2020. Due to implementation patients will be enrolled from November 1, 2020 with planned end of inclusion, April 1, 2022. Follow-up will be concluded on May 1, 2022. The primary analysis will be conducted when the last patient has been followed for 30 days and data is available, which is expected to be November 2022.

Study design;

Hospital	1. sep-20	1. okt-20	1. dec-20	1. feb-21	6. april-21	1. juni-21	1. aug-21	1. okt-21	1. dec-21	1. feb-22	1. april-22
Nykøbing Falster Sygehus											
Herlev & Gentofte Hospital											
Sjællands Universitetshospital											
Bispebjerg & Frederiksberg Hospital											
Nordsjællands Hospital											
Slagelse Sygehus, Bomholms Hospital											
Hvidovre & Amager & Glostrup Hospital											
Holbæk Sygehus											
	Baseline										Follow-up
Censureringsperiode											
Studieperiode											
Follow-up periode, 30 dage											

Figure 1: Cluster-randomised step-wedged" design

Note: There was a break between implementation at Bispebjerg og Nordsjaelland

The reason for the break was organisational challenges due to summer holidays with lower staffing in that period.

Inclusion/Exclusion criteria

Eligible Emergency departments

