- 1. Located in the Capital Region or Region Zealand in Denmark
- 2. Arrival of acutely admitted patients at the on-site Emergency department
- 3. Systemised use of Triage

Patient inclusion criteria

1. ≥18 years at contact to participating emergency department

Patients will be included at the first admission in the study period (index admission) and will remain in this group (intervention/control) for a follow-up period of 30 days.

All subsequent admissions (readmissions) will be ignored with regards to treatment group (i.e., you stay in the group you were first admitted into).

Exclusion

- Patients presenting in the ED with minor injuries (e.g. sprained ankle or minor cuts/abrasions) as they are triaged as blue (level 5) in both systems which typically precludes measurement of vital signs
- 2. Patient admitted directly to specialty ward (without contact to the emergency department)

Definition of clusters

Eligible hospitals can consist of one or two units. A hospital is defined based on its administrative organisation and catchment area. Each hospital will generate one cluster and two (time) periods (control and intervention). See schematic figure 1

Randomisation

Prior to the study start participating clusters will be randomised to start as either intervention or control. Eight clusters are available. The randomisation were performed using computer-generated numbers.

Ethics

The study was presented to the Regional Ethics Committee, who decided that no formal approval was needed in accordance with Danish law. Data management has been approved by the Danish Data Protection Agency (ID: P-2022-405).

Data:

The first 30 days after implementation of I-DEPT will be censored to minimize carry over effect. At follow-up (30 days after inclusion of last patient) the following data is collected from the National Patient Registry (NPR) and the electronic patient journal system Sundhedsplatformen:

- Contacts with the hospital system in the trial period.
- Information regarding admissions (date, time and place of admission and discharge, admission disrupted by patient).

- Information on vital signs and triage level
- Diagnoses (follow-up during study period, historical and in relation to index admission).
- Date of death or emigration (only very few cases of emigration are expected).

Outcomes:

Following outcomes are registered at clinicaltrials.gov (NCT04571021) on September 30, 2020

I-DEPT= Intervention

DEPT = Control

Primary outcome:

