• All-cause mortality within 30 days following triage in the index admission by noninferiority (I-DEPT vs. DEPT)

Secondary outcomes

- All-cause mortality within 2 days following triage in the index admission (I-DEPT vs. DEPT)
- Distribution of patients within triage categories (I-DEPT vs. DEPT) including all-cause mortality within 30-days
 - There are four categories in both triage algorithms used in this study: (green (least urgent), yellow, orange, and red (most urgent))
- Patients in the orange triage category (I-DEPT vs. DEPT) including all-cause mortality within 30-days
 - Number of patients assigned to the orange category previous study showed a significant decrease in this patient group
- Doctor assessment (I-DEPT vs. DEPT)
 - Time from triage to arrival of a doctor Note* Timestamp for arrival of doctor need to be discussed
- Length of stay (I-DEPT vs. DEPT)
 - The total number of days admitted to a hospital within 30 days
- Time in the Emergency Department (I-DEPT vs. DEPT)

- Time spent in the Emergency department from triage to either admission, transfer or discharge
- Patients left without being seen (I-DEPT vs. DEPT)
 - Number of patients leaving the Emergency Department without being assessed by a doctor
- Number of admissions to ICU (I-DEPT vs. DEPT) within 24 hours

Additional secondary outcomes – added July 2022

- Days alive out of hospital within 30 days after admission (I-DEPT vs. DEPT)
- Analyses of primary and secondary outcomes will be repeated with 60 days of censoring after implementation.

[figure not shown]
Additional Post-hoc analyses – added January 2023

- Doctor assessment (I-DEPT vs. DEPT) Time from triage to arrival of a doctor – Note* Timestamp for arrival of doctor need to be discussed – divided into triage groups.
- Analyses of primary and secondary outcomes will be repeated with 90 days of censoring after implementation.

Statistical plan for main outcome paper

Consort diagram:

Schematic consort diagram - following will be reported

Baseline description of groups:

Table 1

	I-DEPT	DEPT	P value
Triage: Red (most urgent), n (%)			p=X
Female, n (%)			
Age, years,			
Systolic Blood Pressure, mmHg			
Heart rate, pr. min			
Respiratory rate, pr. min			
Arterial oxygen saturation, %			
Temperature, degrees Celsius			
Triage: Orange, n (%)			p=X
Female, n (%)			
Age, years,			
Systolic Blood Pressure, mmHg			
Heart rate, pr. min			
Respiratory rate, pr. min			
Arterial oxygen saturation, %			

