Cumulative incidence plots (1-survival) will be calculated using the Kaplan-Meier method and presented with Hazard Ratio and 95% Confidens interval and adjusted for the same variables as the main analysis.

Additional cox regression censoring for "Do not resuscitate order" will also be performed.

Sensitivity analyses of the primary endpoint:

In addition to the ITT analysis, a per-protocol analysis will be performed. In this analysis, interventional patients with missing or incomplete triage will be excluded.

Subgroup analyses of primary endpoint:

The primary outcomes will be calculated for the following subgroups, including a test for interactions.

Results will be presented with distribution n (%) and Odds Ratio with a 95% Confidens interval and illustrated in a Forrest plot and/or Cumulative incidence plots (1-survival) will be calculated using the Kaplan-Meier method.

Following subgroups are planned:

- Triage groups (green to red)
- Age (\leq 39 years, 40 to 69 years, \geq 70 years)
- Medical specialties
- Surgical specialties

Secondary endpoints:

Patients in the orange triage category (I-DEPT vs. DEPT) – including all-cause mortality within 30days:

Main analysis

Same as primary outcome:

Logistic regression that accounts for clustering with adjustment for hospital ID, age, and sex,

period

Results will be presented with distribution n(%) and Odds Ratio with a 95% Confidens interval

Doctor assessment (I-DEPT vs. DEPT)

Time from triage to arrival of a doctor

Main analysis

Distribution will be investigated with Boxplot

Cox regression following the same adjustment principles as for the primary outcome (age, sex, hospital id, period)

Results will be presented with Hazard ratio with a 95% Confidens interval

Length of stay (I-DEPT vs. DEPT)

- The total number of days admitted to a hospital within 30 days

Main analysis

Distribution will be investigated with Boxplot

Linear regression following the same adjustment principles as for the primary outcome (age, sex, hospital id, period?)

Results will be presented with mean days (SD or Interquarentile range) for both groups and difference in hours with a 95% Confidens interval

Time in the Emergency Department (I-DEPT vs. DEPT)

- Time spent in the Emergency department from triage to either admission, transfer or discharge

Main analysis

Linear regression following the same adjustment principles as for the primary outcome (age, sex, hospital id, period?)

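### Assigned triage group is used as a treatment-effect subgroup for 30-day mortality, although each arm's own triage system assigns it

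*SAP*

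**What the plan says.** Under 'Subgroup analyses of primary endpoint' the SAP states: "The primary outcomes will be calculated for the following subgroups, including a test for interactions". Results are to be given as odds ratios with 95% confidence intervals, in a forest plot and/or cumulative incidence plots. The first subgroup listed is "Triage groups (green to red").

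The two arms arrive at that group differently:

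- **I-DEPT** ('Short summary') starts from a vital-sign score, which is then adjusted by the nurse, "who can either up-triage (up to 2 steps) or down-triage (1 step) according to clinical assessment".
- **DEPT** ('Control') combines presenting complaint and vital-sign cut-offs, and "the final triage level is determined by the most urgent triage level assigned".

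The 'Outcomes' section ("Following outcomes are registered at clinicaltrials.gov (NCT04571021) on September 30, 2020") makes the distribution across triage categories a secondary outcome. It also lists "Patients in the orange triage category (I-DEPT vs. DEPT) including all-cause mortality within 30-days", with the explanatory line "Number of patients assigned to the orange category previous study showed a significant decrease in this patient group".

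For the orange endpoint, the analysis under 'Secondary endpoints' is given as "Same as primary outcome": the logistic model accounting for clustering and adjusted for hospital, age, sex and period.

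**The concern.** A treatment-effect subgroup has to be defined by something the treatment does not determine. Age meets that condition. Assigned triage group does not: it is set after allocation, by the intervention in one arm and by the comparator in the other. A patient labelled orange under DEPT because of the presenting complaint may be yellow under I-DEPT, and the nurse may move another patient up into orange. The SAP itself cites an earlier study in which the orange group shrank, so a difference in membership is to be expected.

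The odds ratio within a category then mixes any real effect with the change in who is in the category. The interaction test asks whether that mixture varies across categories, which is not a test of effect modification. A forest-plot row could be read as harm or benefit at that level of urgency when it shows only that the two systems sort patients differently.

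The orange endpoint has a second difficulty. Both the number assigned and 30-day mortality are listed as outcomes, but the analysis section does not say which of the two the regression models. If it models mortality among orange patients, the same bias applies.

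**Working it through.** The SAP gives no category sizes, category mortality, flow between categories or sample size, so there is no stated figure to reproduce. The calculation below holds every patient's risk equal in the two arms and changes only the label. **All shares, risks, flows and sample sizes are assumptions, and all odds ratios are crude.** Throughout, OR = [p₁/(1−p₁)] / [p₀/(1−p₀)], with p₁ the category risk under I-DEPT and p₀ under DEPT.

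**1. Outflow from orange only.** Orange mortality under DEPT is 5%, and 30% of orange patients leave, with mortality m. Remaining orange risk = (0.05 − 0.30m)/0.70.

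| m | Orange risk, I-DEPT | OR |
|---|---|---|
| 2% | 0.0629 | 1.27 |
| 5% | 0.0500 | 1.00 |
| 8% | 0.0371 | 0.73 |

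The direction depends on who leaves.

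**2. Four categories.** Under DEPT, green/yellow/orange/red hold 30/40/25/5% of patients with mortality 1/2/5/20%. Pooled mortality = 0.0030 + 0.0080 + 0.0125 + 0.0100 = 0.0335.

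*Scenario A, unequal shifts.* 30% of orange (0.075 of all patients) moves to yellow at 2% mortality; 5% of yellow (0.020 of all patients) moves to orange at 5%.

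- Yellow: (0.0080 − 0.0010 + 0.0015)/(0.40 − 0.020 + 0.075) = 0.0085/0.455 = 0.0187
- Orange: (0.0125 − 0.0015 + 0.0010)/(0.25 − 0.075 + 0.020) = 0.0120/0.195 = 0.0615
- Green and red unchanged; pooled 0.0030 + 0.0085 + 0.0120 + 0.0100 = 0.0335

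*Scenario B, shifts of similar size.* 30% of each level moves down one; the movers have mortality 12% (from red), 3% (from orange) and 1.4% (from yellow).

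- Green: (0.0030 + 0.12 × 0.014)/0.42 = 0.0111
- Yellow: (0.0080 − 0.00168 + 0.075 × 0.03)/0.355 = 0.0241
- Orange: (0.0125 − 0.00225 + 0.015 × 0.12)/0.19 = 0.0634
- Red: (0.0100 − 0.0018)/0.035 = 0.2343
- Pooled again 0.0335

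| | Green OR | Yellow OR | Orange OR | Red OR |
|---|---|---|---|---|
| A | 1.00 | 0.93 | 1.25 | 1.00 |
| B | 1.12 | 1.21 | 1.29 | 1.22 |

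**3. What the interaction test would show.** The inverse-variance heterogeneity statistic Q of the four log odds ratios (3 df), ignoring clustering and adjustment:

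| | 20,000 per arm | 50,000 per arm |
|---|---|---|
| A | Q = 4.70, p = 0.20 | Q = 11.75, p = 0.008 |
| B | Q = 0.60, p = 0.90 | Q = 1.50, p = 0.68 |

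A can produce a significant interaction with no effect in any patient. B does not, yet all four odds ratios exceed 1. Even at 20,000 per arm the crude 95% interval for orange excludes 1 in both scenarios (1.04 to 1.50 in A, 1.07 to 1.54 in B). A flat interaction test is therefore no safeguard.

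**4. A second set of assumptions.** Same shares, mortality 1/2.5/6/20% (pooled 3.8%), with 10, 20 or 40% of orange relabelled yellow and carrying yellow-level risk: orange OR 1.07, 1.16 or 1.42, yellow 1.00. If the movers have a risk midway between yellow and orange, 40% moved gives orange 1.21 and yellow 1.14, so both categories look worse. The mechanism does not depend on one choice of inputs.

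**The case against.** The strongest reply is that mortality by category is a stated aim. The trial compares the systems on risk prediction as well as outcomes, and an arm-by-category term also tests whether the mortality gradient across categories differs between systems. Read that way, the significant result in scenario A correctly detects different sorting, and a label would be enough. On this view, making orange mortality descriptive also takes planned inference away from a listed secondary outcome. That the aim is legitimate stands. But the SAP places the test among the subgroup analyses of the primary endpoint, beside age and specialty, where an interaction means effect modification. Descriptive reporting can still carry an interval for each arm.

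The sizes are also open to challenge. They rest wholly on assumptions, and only one of the four interaction results above is significant. That one needs 50,000 per arm and no clustering; with an assumed variance inflation of 1.5 or 2, its p of 0.008 becomes 0.05 or 0.12. This is fair: the mechanism is certain, the size in this trial is unknown.

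Adjustment for age, sex, hospital and period may absorb part of the shift in case mix, but the sorting runs through vital signs, complaint and nurse judgement, none of which is in the model. Table 1 will let readers see the shift without correcting it.

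Finally, the orange section can be read as modelling mortality and merely reporting the count. That is a natural reading, but it is the one to which the bias applies.

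**Conclusion.** The concern holds. Assigned triage group is an outcome of the comparison and cannot also define a subgroup for its treatment effect on mortality. This follows from the SAP's own description of the two systems and needs no numerical assumption.

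The size does need assumptions. With plausible but invented shares and risks, crude orange odds ratios run from 0.73 to 1.42 with no change in any patient's risk. The direction is not fixed, and the interaction test may or may not react.

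The primary non-inferiority analysis of all patients is unaffected and no decision rule hangs on this subgroup. The change should be made, but it does not threaten the main conclusion.

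**What to change.** 1. Take assigned triage group out of the treatment-effect subgroups and the interaction test.
2. Keep 30-day mortality by assigned category in each arm, with a statement that it shows how each system sorts risk and is not a treatment effect.
3. For the orange endpoint keep both parts: analyse assignment to orange (yes/no) among all patients with the primary model, and report 30-day mortality among orange patients descriptively.
4. If a severity subgroup is wanted, define it by one vital-sign score computed identically in both arms from the recorded vital signs, for example the I-DEPT score before the nurse's adjustment. State a missing-data rule for it, because 'Handling of missing data' provides only for variables with more than 5% missing.

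Items 1 to 3 cost SAP wording only. One planned subgroup test is lost and orange mortality becomes descriptive; no registered outcome is dropped. Item 4 is optional and costs more. The score must be specified in advance and shown to be computable from DEPT records. Because vital signs are recorded during each arm's own triage, missingness may differ by arm and bring some selection of its own.

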Temperature, degrees Celsius			
Triage: Yellow, n (%)			р=Х
Female, n (%)			,
Age, years,			
Systolic Blood Pressure, mmHg			
Heart rate, pr. min			
Respiratory rate, pr. min			
Arterial oxygen saturation, %			
Temperature, degrees Celsius			
Triage: Green (least urgent), n (%)			p=X
Female, n (%)			
Age, years,			
Systolic Blood Pressure, mmHg			
Heart rate, pr. min			
Respiratory rate, pr. min			
Arterial oxygen saturation, %			
Temperature, degrees Celsius			
Missing triage			р=X

Table of summary statistics for patients for each group (intervention or control) will be presented for each triage of the four triage groups with baseline variables shown in Table 1.

Continuous variables will be summarized with mean and standard deviation or interquartile range (based on non-missing sample size).

Categorical variables will be reported as frequency and percentages (based on non-missing sample size) and number of missing values.

Categorical variables will be tested with chi-square.

Primary outcome analysis:

The primary outcomes will be an analysis of all-cause mortality within 30 days.

Patients will be followed as one cohort and data will be analysed as randomised and in accordance with the intention-to-treat principle.

- Patients (18+) will be included at the first admission at the participating hospitals in the study period (index admission) and will remain in this group (intervention/control) for follow-up of 30 days.
- Admission is defined as any contact to an emergency department where a Triage is performed
- Any patient lost to follow-up will be censored at the last time known to be alive.

Censored periods: Each period will start with 30 days of implementation, and the end of the study is followed by an observation period of 30 days. Periods of implementation and observation will be censored in the analyses (patients admitted in these periods will not be included in the analyses).

Main analysis

Logistic regression that accounts for clustering with adjustment for hospital ID, age, and sex, period (e.g., calendar month).

Results will be presented with distribution n (%) and Odds Ratio with a 95% Confidens interval and Risk difference with 95% Confidens interval. The assumption is that the actual intervention effect is 0. Non-inferiority will be assessed based on the risk difference with a non-inferiority margin (Δ) of 0.5%.

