Results will be presented with mean hours (SD eller Interquarentile range) for both groups and difference in hours with a 95% Confidens interval

Patients left Emergency department without being seen (I-DEPT vs. DEPT)

- Number of patients leaving the Emergency Department without being assessed by a doctor

Main analysis

Analysis – Logistic regression that accounts for clustering with adjustment for hospital ID, age, and sex, period??

Results will be presented with distribution n (%) and Odds Ratio with a 95% Confidens interval

Number of admissions to ICU (I-DEPT vs. DEPT) within 24 hours

Main analysis

Analysis - Logistic regression that accounts for clustering with adjustment for hospital ID, age, and sex, period

Results will be presented with distribution n (%) and Odds Ratio with a 95% Confidens interval

Days out of hospital within 30 days after admission (I-DEPT vs. DEPT)

Main analysis

Distribution will be investigated with Boxplot

Linear regression following the same adjustment principles as for the primary outcome (age, sex, hospital id, period?)

Results will be presented with mean days (SD or Interquarentile range) for both groups and difference in hours with a 95% Confidens interval

Handling of missing data:

The primary outcome analysis should be subject to no or little missing data as it is based on Danish register data. Patients lost to follow-up (tourists) will be censored at the last registration. If more than 5% of data is missing on a variable included in planned analyses, multiple imputation will be introduced.

Additional Post-hoc analyses (planned ultimo July 2022)

Analyses of primary and secondary outcomes will be repeated with 60 days of censoring after implementation.

Analyses of primary and secondary outcomes will be repeated with 90 days of censoring after implementation.

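### The SAP names clustering only for its logistic models; the Cox and linear models carry over only the covariates, so fitted as listed their confidence intervals are too narrow whenever hospital-by-month correlation is positive

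*SAP*

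**What the plan says.** The SAP's Main analysis of the primary outcome specifies "Logistic regression that accounts for clustering with adjustment for hospital ID, age, and sex, period (e.g., calendar month". That sentence makes two separate statements: clustering is accounted for, and certain covariates are adjusted for. The logistic models for the orange triage category, patients leaving without being seen and ICU admission repeat both parts ("Logistic regression that accounts for clustering with adjustment for hospital ID, age, and sex").

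Five other analyses do not:

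- **Time from triage to doctor** (Secondary endpoints, Doctor assessment): "Cox regression following the same adjustment principles as for the primary outcome (age, sex, hospital id, period".
- **Length of stay, time in the emergency department, days out of hospital** (Secondary endpoints): each reads "Linear regression following the same adjustment principles as for the primary outcome (age, sex, hospital id, period", and in each the word period is followed by a question mark.
- **Hazard ratio for 30-day mortality** (Primary outcome analysis, with the cumulative incidence plots): "presented with Hazard Ratio and 95% Confidens interval and adjusted for the same variables as the main analysis".

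The additional Cox regression that censors at a do-not-resuscitate order names neither covariates nor clustering. The section Definition of clusters makes each hospital one cluster with a control and an intervention period, and Randomisation gives eight clusters.

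**The concern.** Treatment is allocated by hospital and calendar time, and its effect is estimated from changes over time within hospitals. A hospital covariate removes stable differences in level between hospitals. A period covariate removes the calendar trend that all hospitals share. Neither removes what is particular to one hospital in one month, such as local staffing, crowding or bed shortage. Patients of the same hospital and month therefore remain correlated, while ordinary linear or Cox standard errors treat them as independent.

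Waiting time, time in the department and length of stay plausibly depend on such local conditions. The SAP itself reports a pause in the rollout because of low summer staffing. If the models are fitted as listed, a difference that is only hospital-month noise could be reported as a clear operational benefit or harm of I-DEPT.

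**Working it through.** **No figure to reproduce.** The SAP states no sample size, intraclass correlation or number of patients per hospital-month. The calculation below therefore uses assumed ranges.

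**Inputs from the SAP.** There are eight hospitals, with hospital and calendar-month effects in the model and the first 30 days after implementation excluded. The switch months are read from the dates of Figure 1 and the note on the break (October and December 2020; February, April, August, October and December 2021; February 2022). This reading is an assumption, because the shading of the figure is not available.

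**Assumed inputs.** *m*, the patients per hospital-month, is 300 to 2000. *r*, the intraclass correlation within hospital-month that remains after hospital and month effects, is 0.0001 to 0.01.

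**Formula.** Scale the patient-level variance to 1.

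- True variance of a hospital-month mean: r + (1 − r)/m = [1 + (m − 1)r]/m.
- Variance under independence: 1/m.
- With equal hospital-months and independent hospital-month effects, the treatment estimate weights the means identically in both cases. So SE ratio = √[1 + (m − 1)r].
- Actual coverage of a nominal 95% interval = 2Φ(1.96/ratio) − 1.

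Two examples:

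- m = 300, r = 0.0001: √(1 + 299 × 0.0001) = √1.03 = 1.01.
- m = 2000, r = 0.01: √(1 + 1999 × 0.01) = √20.99 = 4.58.

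| m | r = 0.0001 | r = 0.001 | r = 0.01 |
|---|---|---|---|
| 300 | 1.01 (94.7%) | 1.14 (91.5%) | 2.00 (67.4%) |
| 1000 | 1.05 (93.8%) | 1.41 (83.4%) | 3.32 (44.6%) |
| 2000 | 1.10 (92.6%) | 1.73 (74.2%) | 4.58 (33.1%) |

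Entries are the SE ratio, with actual coverage in brackets.

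**Autocorrelated months.** With a month-to-month autocorrelation of 0.8 in the hospital-month effects, the ratio runs from 1.03 (m = 300, r = 0.0001) to 6.8 (m = 2000, r = 0.01). Starting the data in September or in November 2020 changes this little.

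**Which remedy works with eight hospitals.** A simulation of the same layout compared three options for nominal 95% intervals:

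- Hospital-clustered variance without correction, normal critical value: about 86% coverage.
- An analysis that assumes independent hospital-month effects: about 74% to 87% when months were in fact autocorrelated at 0.8.
- Hospital-clustered variance with a small-sample correction and a t distribution on 7 (= 8 − 1) degrees of freedom: 93% to 97%.

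**The case against.** The strongest reply is that the Cox and linear lines for the secondary outcomes refer back to the principles of the primary analysis, and those include accounting for clustering. The bracket may be shorthand for the covariates. This reading is possible, and the SAP nowhere says that patients will be treated as independent. A reader might infer that clustering was deliberately left out; the text does not establish that. However, the primary sentence separates clustering from adjustment, and the bracket repeats only the second part. A programmer could fit ordinary regression with the listed covariates and comply with the text. The benign reading is weakest for the mortality hazard ratio, which takes over variables only.

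A second reply is that the logistic models are no model to copy. How they account for clustering is undefined, and a hospital random intercept would satisfy the phrase while leaving hospital-by-month correlation untouched. This stands, so carrying the phrase over would not be enough.

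A third reply is that the size is unknown. This also stands: at r = 0.0001 the understatement is 1% to 10% with independent months. The formula is also for a linear model; for the two Cox analyses it indicates direction only.

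**Conclusion.** The SAP commits to handling clustering in its logistic models only. For four secondary outcomes and the mortality hazard ratio it lists covariates, and those covariates do not absorb hospital-by-month correlation. Fitted as listed with independent errors, the intervals are too narrow whenever that correlation is positive.

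A reader might infer that they will be much too narrow. The SAP does not support that, because the understatement ranges from negligible to several-fold over the assumed values and nothing in the SAP narrows the range. A reader might also infer that the primary conclusion is at risk from this point. It is not, since non-inferiority is judged on the risk difference from the logistic model. The matter concerns secondary and supportive analyses, and should be settled before they are reported.

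**What to change.** In the five places, replace the model sentence by: *linear (or Cox) regression with adjustment for hospital ID, age, sex and period (calendar month), with variance clustered on the randomised hospital and a small-sample correction for eight clusters (for example a bias-reduced or jackknife cluster-robust variance with a t distribution on 7 degrees of freedom)*. Delete the question mark after period, so that adjustment for calendar time is no longer open.

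Uncorrected hospital-clustered variance should not be the only protection, and neither should a hospital-by-month random effect that assumes independent months. In the simulation above, neither kept its nominal coverage.

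The cost is a few sentences in the SAP, a little more model code and, in general, wider intervals. No additional data are needed.
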